##### 4.1.3 Patients must be eligible for one of two cohorts:

**Cohort 1 (FLT3 inhibitor failure cohort)** in FLT3-ITD and/or FLT3-D835 mutated relapsed/refractory AML who have failed therapy with up to two prior salvage regimens (SCT or stem cell therapy for patients who previously underwent SCT/stem cell therapy in remission will not be considered a salvage regimen) and have previously been exposed at least one prior FLT3 inhibitor.

**Cohort 2 (FLT3 inhibitor naive cohort)** in FLT3-ITD and/or FLT3-D835 mutated relapsed/refractory who have failed therapy with up to two prior salvage regimens (SCT or stem cell therapy for patients who previously underwent SCT/stem cell therapy in remission will not be considered a salvage regimen) with no prior exposure to any FLT3 inhibitor.

- 4.1.4 Age  $\geq$ 18 years.
- 4.1.5 ECOG Performance Status  $\leq$ 2.
- 4.1.6 Patients should have estimated life expectancy of  $>$ 3 months at study entry.
- 4.1.7 Adequate hepatic (serum direct bilirubin  $\leq$  2.0 x upper limit normal (ULN) (or  $\leq$  3.0 x ULN if deemed to be elevated due to leukemia), alanine aminotransferase and/or aspartate transaminase  $\leq$  3.0 x ULN (or  $\leq$  5.0 x ULN if deemed to be elevated due to leukemia), and renal function (creatinine  $\leq$  2.0 mg/dL).
- 4.1.8 Patients must provide written informed consent.
- 4.1.9 In the absence of rapidly progressing disease, the interval from prior treatment to time of initiation of selinexor and sorafenib administration will be at least 2 weeks for cytotoxic agents or at least 5 half-lives for cytotoxic/noncytotoxic agents. The half-life for the therapy in question will be based on published pharmacokinetic literature (abstracts, manuscripts, investigator brochure's, or drug-administration manuals) and will be documented in the protocol eligibility document. The use of chemotherapeutic or anti-leukemic agents is not permitted during the study with the following exceptions: (1) intrathecal (IT) therapy for patients with controlled CNS leukemia at the discretion of the PI and with the agreement of the Sponsor. Controlled CNS leukemia is defined by the absence of active clinical signs of CNS disease and no evidence of CNS leukemia on the most recent 2 simultaneous CSF evaluations. (2) Use of one dose of cytarabine (up to 2 g/m^2) or hydroxyurea for patients with rapidly proliferative disease is allowed before the start of study therapy and for the first four weeks on therapy. These medications will be recorded in the case-report form.
- 4.1.10 Baseline ejection fraction must be  $\geq$  40%.

- 4.1.11** Females must be surgically or biologically sterile or postmenopausal (amenorrheic for at least 12 months) or if of childbearing potential, must have a negative serum or urine pregnancy test within 72 hours before the start of the treatment.
- 4.1.12** Women of childbearing potential must agree to use an adequate method of contraception during the study and until 3 months after the last treatment. Males must be surgically or biologically sterile or agree to use an adequate method of contraception during the study until 3 months after the last treatment.

Adequate methods of contraception include:

- Total abstinence when this is in line with the preferred and usual lifestyle of the patient. Periodic abstinence (e.g., calendar, ovulation, symptothermal, post-ovulation methods) and withdrawal are not acceptable methods of contraception.
- Female sterilization (have had surgical bilateral oophorectomy with or without hysterectomy) or tubal ligation at least six weeks before taking study treatment. In case of oophorectomy alone, only when the reproductive status of the woman has been confirmed by follow up hormone level assessment
- Male sterilization (at least 6 months prior to screening). For female patients on the study, the vasectomized male partner should be the sole partner for that patient
- Combination of any of the two following (a+b or a+c or b+c)
  - a. Use of oral, injected or implanted hormonal methods of contraception or other forms of hormonal contraception that have comparable efficacy (failure rate <1%), for example hormone vaginal ring or transdermal hormone contraception
  - b. Placement of an intrauterine device (IUD) or intrauterine system (IUS)
  - c. Barrier methods of contraception: Condom or Occlusive cap (diaphragm or cervical/vault caps) with spermicidal foam/gel/film/cream/ vaginal suppository

In case of use of oral contraception, women should have been stable on the same pill before taking study treatment.

**Note:** Oral contraceptives are allowed but should be used in conjunction with a barrier method of contraception due to unknown effect of drug-drug interaction.

Women are considered post-menopausal and not of child bearing potential if they have had 12 months of natural (spontaneous) amenorrhea with an appropriate clinical profile (e.g.

age appropriate, history of vasomotor symptoms) or have had surgical bilateral oophorectomy (with or without hysterectomy) or tubal ligation at least six weeks ago. In the case of oophorectomy alone, only when the reproductive status of the woman has been confirmed by follow up hormone level assessment is she considered not of child bearing potential.

## 4.2 Exclusion Criteria

- 4.2.1 Patients with known allergy or hypersensitivity to selinexor, sorafenib or any of its components.
- 4.2.2 Subject has concurrent, uncontrolled medical condition, laboratory abnormality, or psychiatric illness, which could place him/her at unacceptable risk.
- 4.2.3 Patients who have had any major surgical procedure within 14 days of Day 1.
- 4.2.4 Patients currently receiving any other standard or investigational therapy for the treatment of AML.
- 4.2.5 Patients unwilling or unable to comply with the protocol.
- 4.2.6 Patients receiving concomitant treatment with strong CYP3A4 inhibitors, unless such drugs are considered critical for the well being of the patient and not adequate alternatives are available. Strong CYP3A4 inhibitors include the following medications: itraconazole, ketoconazole, miconazole, voriconazole; amprenavir, atazanavir, fosamprenavir, indinavir, nelfinavir, ritonavir; ciprofloxacin, clarithromycin, diclofenac, doxycycline, enoxacin, isoniazid, ketamine, nefazodone, nicardipine, propofol, quinidine, telithromycin.
- 4.2.7 Patients with any severe gastrointestinal or metabolic condition that could interfere with absorption of oral medications.
- 4.2.8 Patients who are in blast transformation of chronic myeloid leukemia (CML). Prior MDS or CMML is acceptable.
- 4.2.9 Patient has a concurrent active malignancy under treatment.
- 4.2.10 Unstable cardiovascular function:
- Symptomatic ischemia, or
  - Uncontrolled clinically significant conduction

abnormalities (i.e., ventricular tachycardia on antiarrhythmic agents are excluded; 1st degree atrioventricular (AV) block or asymptomatic left anterior fascicular block/right bundle branch block (LAFB/RBBB) will not be excluded), or

- Congestive heart failure (CHF) NYHA Class  $\geq 3$ , or
- Myocardial infarction (MI) within 3 months.
- Left ventricular ejection fraction  $< 40\%$ .
- Hypertension  $> 140$  mm Hg systolic or  $> 90$  mm Hg diastolic with or without antihypertensive therapy.

- 4.2.11** Uncontrolled infection at the time of enrollment. Infections controlled on concurrent anti-microbial agents are acceptable, and anti-microbial prophylaxis per institutional guidelines is acceptable.
- 4.2.12** Known active hepatitis B virus (HBV) or C virus (HCV) infection; or known to be positive for HCV ribonucleic acid (RNA) or HBsAg (HBV surface *antigen*).
- 4.2.13** Known human immunodeficiency virus (HIV) infection.
- 4.2.14** Female subjects who are pregnant or breastfeeding.
- 4.2.15** Acute promyelocytic leukemia.
- 4.2.16** Any medical condition, which in the investigator's opinion, could compromise the patient's safety.

## **5.0 TREATMENT PLAN:**

### **5.1 Schedule**

All patients will be registered through CORE/PDMS.

5.1.1 Selinexor will be administered orally twice a week (e.g. Monday/Wednesday or Tuesday/Thursday or Wednesday/Friday) for 3 weeks of a 28-day cycle. Selinexor will not be dosed the last week of the cycle (week 4). After initiation of sorafenib on cycle 1 day 1, sorafenib will be administered orally daily twice continuously for the duration of the study with no interruptions unless there are adverse events as described in Section 5.2 below. Sorafenib doses will be separated by intervals of approximately 12 hours (+/- 2 hours). Sorafenib will be administered without food, at least 1 hour before or 2 hours after eating. If a dose is missed, the

next dose will not be increased to account for missing a dose. The patient will take the next regular dose at the scheduled time. Patients will receive one cycle of therapy every 28 days (+/- 7 days).

On the day when both drugs, Selinexor and Sorafenib, will be administered:

- Selinexor needs to be taken with food.
- Sorafenib should not be taken with food. Therefore, patient should take Sorafenib at least 1 hour before eating or 2 hours after eating.

**5.1.1.1** Cycles may be started early (but not earlier than day 21) for patients with active disease if judged in the best interest of the patient.

\*For the phase I, DLT defining period is 28 days. As such, cycle 2 should not be started before 28 days for the patients being treated on the phase I cohort to allow for adequate evaluation of DLTs.

**5.1.1.2** Subsequent cycles may be delayed for recovery of toxicity or other medical conditions. Delays in start of subsequent cycles greater than 8 weeks will be acceptable only for patients who are deriving clinical benefit and after discussion with the principal investigator and the sponsor of potential risk/benefit ratio and complete documentation of the degree of clinical benefit and reason for continuation on this regimen.

**5.1.1.3** In instances where one drug has to be discontinued transiently because of safety, the administration of the other drug may continue as scheduled. If the drug that is held can resume at a later time, no doses will be made up and the administration will follow the originally defined schedule calendar according to the drug that was continued.

**5.1.1.4** For patients who discontinue therapy, the reason for treatment discontinuation will be documented.

**5.1.1.5** Patients must receive at least 4 doses of selinexor and at least 44 doses of sorafenib during the first 28 days on trial (i.e. during cycle 1) to be evaluated for DLT. Patients who receive less than 4 doses of selinexor and/or less than 44 doses of sorafenib during the first 28 days on trial will not be evaluable for DLT. Patients not evaluable for DLT will be replaced. These patients may continue therapy on trial

after discussion with the PI if they are having clinical benefit and the reasons for continuation and potential benefit/risk profile for the patient must be clearly documented in the medical records.

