*Preliminary Safety Results:* Grade 3/4 TEAEs that were reported in > 3 patients include: fatigue (18%), and nausea (8%). Grade 3/4 thrombocytopenia (15%) and neutropenia (11%) were observed, however a majority of patients enrolled with baseline high-grade thrombocytopenia and neutropenia as part of progressive disease (which is associated with reduced hematopoietic function). The most

common Grade 1/2 TEAEs were diarrhea (82%), anorexia (78%), nausea (74%), and fatigue (65%). No DLTs were reported during the dose escalation phase, however due to SAEs that were seen at 85 mg/m^2 in study KCP-330-002, a maximum allowable dose of 70 mg/m^2 twice weekly was assigned for this and future studies. The anticipated selinexor dose for patients in future AML studies will be 80-100 mg (35-60 mg/m^2) twice weekly. For details of overall safety results in the AML patients and in all hematologic clinical studies please see the attached IB (Appendix C)

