### 3.2 Study Design

- The phase I portion is aimed at finding the MTD and RP2D of the combination drugs. We will use the standard “3+3” design. The target dose is dose level +1, and the starting dose will be dose level 0. The first 3 patients on study will receive dose level 0.
- Other dose levels will be used for dose adjustments for toxicity during therapy (Table 3).
- Prior to advancing/changing dose levels, a cohort summary will be completed and submitted to the IND Office Medical Monitor for review and approval. A copy of the cohort summary should be placed in the Investigator’s Regulatory Binder under “sponsor correspondence”.
- The dosing schema is shown in Table 3 below.

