**Table 5 – Specific supportive Care and Dose Adjustment Guidelines for Selinexor-Related Toxicities**

Toxicity and Intensity	Supportive treatment	Selinexor Dose Modification	
Fatigue (common)			
Grade 1	Rule out other causes of fatigue. Consider addition of 4-8 mg dexamethasone or equivalent on the day after selinexor. Insure adequate caloric intake and assess volume status.	Maintain dose.	
Grade 2	Rule out other causes of fatigue. Consider addition of 4-8 mg dexamethasone or equivalent on the day after selinexor. Insure adequate caloric intake and assess volume status. For additional support see NCCN guidelines.	Maintain dose. Consult medical monitor for additional option such as temporary dose reduction or short dose interruptions.	
Grade 3	See guidelines for Grade 2 fatigue	Interrupt selinexor dosing until resolved to Grade $\leq$ 2, For first occurrence of Grade 3, if adequate supportive care resulted in fatigue improving to Grade $\leq$ 1 within 7 days, restart selinexor at current dose. Otherwise, restart selinexor at one dose level below (Table 3).	
Anorexia or Weight loss			

Toxicity and Intensity	Supportive treatment	Selinexor Dose Modification	
Grade 1	
Rule out other causes of anorexia.
 
Assess dietary options (e.g., try a variety of other foods).
 
Add high-calorie supplements (e.g., Ensure®).
 
Consider addition of 4-8 mg dexamethasone or equivalent on the day after selinexor.
	Maintain dose.	
Grade 2	
Rule out other causes of anorexia.
 
Assess dietary options (e.g., try a variety of other foods).
 
Add high-calorie supplements (e.g., Ensure®).
 
Consider addition of 4-8 mg dexamethasone or equivalent on the day after selinexor.
 
Consider megestrol acetate 80-400 mg daily.
 
Consider anabolic steroids such as oxandrolone, or dronabinol (Marinol®) or other cannabinoid, mainly for patients who can't tolerate steroids or at high risk to progress.
 
For additional supportive care see NCCN guidelinesb
	Selinexor may be skipped intermittently while supportive medications are instituted, usually for <1 week.	
Grade 3	See guidelines for Grade 2 anorexia.	
Interrupt dosing with selinexor.
 
Restart selinexor at 1 dose level reduction (Table 3) once anorexia resolves to Grade <math>\leq 2</math> and patient is clinically stable.
	

Toxicity and Intensity	Supportive treatment	Selinexor Dose Modification	

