Grade 3 (120-125 nM) or Grade 4 or any Grade 3 with Symptoms	Correct sodium as per institutional guideline Initiate salt supplementation two-three times per day.	Hold selinexor until resolved to Grade $\leq 1$ ( $\geq 130$ nM) then reduce selinexor dose by 1 level (Table 3). For Grade 3 hyponatremia, if serum sodium stabilizes to grade $\leq 1$ for at least 4 weeks, then original dose of selinexor may be resumed.	
Diarrhea (common)			
Grade 1+2	Diet recommendation as per guidelines (Benson, 2004) d . Institute standard anti-diarrheal therapy. After the first occurrence of diarrhea, loperamide 2 mg should be considered prophylactically approximately 1-2 hours before the administration of selinexor and repeated every 4 hours for the first 12 hours.	For Grade 2 only, reduce selinexor one dose level (Table 3) until resolved to $\leq$ Grade 1, then re-start at the current dose level.	

Toxicity and Intensity	Supportive treatment	Selinexor Dose Modification	
Grade 3	
Institute IV fluids                      Diet recommendation as per guidelines (Benson, 2004)d.
 
Institute standard anti-diarrheal therapy.
 
Once the symptoms resolve to <math>\leq</math>Grade 1, loperamide 2 mg should be considered prophylactically approximately 1-2 hours before the administration of selinexor and repeated every 4 hours for the first 12 hours.
	
Delay selinexor until resolved to <math>\leq</math> Grade 1, then reduce selinexor dose by one dose level (Table 3).
 
If diarrhea stabilizes for at least 4 weeks at Grade <math>\leq</math>1, then original dose of selinexor may be resumed.
	
Grade 4	
Rule out other causes of diarrhea, including infectious agents. In case of opportunistic infection, withdraw all steroids (with tapering if medically appropriate) until culture is negative. Follow institutional guidelines for Grade 4 diarrhea.
	
Delay selinexor until resolved to <math>\leq</math> Grade 1, then reduce selinexor dose by one dose level (Table 3).
	
Other selinexor-related adverse events*			
Grade 1 or 2	
Initiate standard supportive care and follow institutional guidelines.
	
Maintain dose.
	
Grade 3	
Initiate standard supportive care and follow institutional guidelines.
	
Delay dose until resolved to Grade <math>\leq</math> 1 or baseline, then reduce by one dose level (Table 3).
	

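### DLT evaluability counts doses and not dose level, so a phase I patient reduced in cycle 1 for a non-DLT toxicity counts as DLT-free at the assigned level

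*Combined protocol and SAP*

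**What the plan says.** Section 5.1.1.5 sets the entry condition for the DLT count: "Patients must receive at least 4 doses of selinexor and at least 44 doses of sorafenib during the first 28 days on trial". The converse is also by number: "Patients who receive less than 4 doses of selinexor and/or less than 44 doses of sorafenib during the first 28 days on trial" are not evaluable and are replaced. Neither sentence mentions milligrams or the assigned level.

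Section 3.2 keeps the lower levels available for toxicity: "Other dose levels will be used for dose adjustments for toxicity during therapy (Table 3"). The only limit on adjustments that reaches cycle 1 is in Section 5.2.1, and it concerns myelosuppression. For toxicity likely related to selinexor, Table 5 of Section 5.2.2 gives the reductions. After grade 3 diarrhea selinexor goes down one level, whatever the length of the episode. After a first grade 3 fatigue or nausea the same dose is resumed only if grade 1 or less is reached within 7 days (fatigue) or 3 days (nausea). For both, the alternative reads "Otherwise, restart selinexor at one dose level below (Table 3").

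Section 3.4 counts grade 3 nausea, vomiting or diarrhea as a DLT only beyond 3 days, and grade 3 fatigue only beyond 5 days, under optimal support. Its replacement rule covers patients who stop treatment for reasons other than toxicity. Sections 3.3, 3.4 and 11.1 do not say how a patient who was reduced but did not stop is counted.

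**The concern.** A 3+3 count assumes that each patient recorded without a DLT was observed on the dose being judged. Here a patient can have a toxicity that moves selinexor down a level, complete the cycle on the lower level, and still be one of the three or six patients who clear the higher one. The MTD and RP2D are the primary objective of phase I, and the RP2D is the dose for up to 40 phase II patients. The margin is thin: under Section 3.3, 2 DLTs in 6 means that the MTD has been exceeded, and 1 in 6 means that it has not. One DLT that failed to appear because the dose had been lowered is enough to change the decision.

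**Working it through.** The plan states no figure on this point to reproduce.

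**1. Planned cycle 1 doses.** Selinexor is given twice weekly "for 3 weeks of a 28-day cycle. Selinexor will not be dosed the last week of the cycle (week 4"), so 2 × 3 = 6 doses, and the minimum of 4 is 4/6 = 67%. For sorafenib, "sorafenib will be administered orally daily twice continuously for the duration of the study", so 2 × 28 = 56 doses, and the minimum of 44 is 44/56 = 79%.

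**2. Events that reduce selinexor but are not DLTs.**
- Grade 3 diarrhea of 3 days or less: Table 5 reduces, and the Section 3.4 threshold is not met.
- Grade 3 nausea that leaves grade 3 within 3 days but does not reach grade 1 in that time: reduced, not a DLT.
- Grade 3 fatigue of 5 days or less that does not reach grade 1 within 7 days: reduced, not a DLT.

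The last grade 3 bullet in Section 3.4 covers only other events, so it does not bring these back in.

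**3. Exposure of a level +1 patient reduced from 100 to 80 mg after dose 1.** Full +1 cycle: 6 × 100 = 600 mg. Full level 0 cycle: 6 × 80 = 480 mg.
- All six doses taken: 100 + 5 × 80 = 500 mg (83%).
- One dose missed: 100 + 4 × 80 = 420 mg (70%).
- Minimum count: 100 + 3 × 80 = 340 mg (57%).

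With at least 44 sorafenib doses, all three patients are evaluable at +1 after a single dose at that level.

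**4. Direction.** If DLT risk does not rise when the dose falls, such patients can only lower the expected DLT count at the assigned level.

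**5. Illustration of size (the risks are assumptions; the documents give none).** For three patients, let q0 be the chance of no DLT and q1 the chance of exactly one. With the same mix in both groups of three, P(at most 1 in 6) = q0² + 2·q0·q1.
- All at 40%: q0 = 0.6³ = 0.216; q1 = 3 × 0.4 × 0.36 = 0.432; P = 0.0467 + 0.1866 = 0.233.
- One of three at 20%: q0 = 0.6 × 0.6 × 0.8 = 0.288; q1 = 2 × 0.4 × 0.6 × 0.8 + 0.6 × 0.6 × 0.2 = 0.456; P = 0.0829 + 0.2627 = 0.346.
- Two of three at 20%: q0 = 0.6 × 0.8 × 0.8 = 0.384; q1 = 0.4 × 0.8 × 0.8 + 2 × 0.6 × 0.2 × 0.8 = 0.448; P = 0.1475 + 0.3441 = 0.492.

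**6. Range.** Let p be the true DLT risk at full dose and f the share of would-be DLTs that early reduction prevents. With r = p(1 − f), P = (1 − r)⁶ + 6r(1 − r)⁵:

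| p | f = 0 | f = 0.10 | f = 0.25 | f = 0.50 |
|---|---|---|---|---|
| 0.33 | 35.8% | 42.7% | 54.0% | 74.1% |
| 0.40 | 23.3% | 30.1% | 42.0% | 65.5% |
| 0.50 | 10.9% | 16.4% | 27.4% | 53.4% |

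**The case against.** The route is narrow. Many grade 3 events are DLTs in their own right, and no reductions for myelosuppression are planned in cycle 1. Several wider readings are tempting, but the documents do not support them.

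- *Table 4 opens the same gap.* In practice it does not. It makes no reduction at grade 1 or 2, and for a first or second grade 3 event it reduces only after 15 to 28 days of persistence. A 15-day sorafenib hold loses 2 × 15 = 30 doses and leaves 56 − 30 = 26, below 44. With selinexor on days 1 and 3 of weeks 1 to 3, a 15-day hold starting after dose 1 or 2 leaves 2 doses, below 4. Those patients are already replaced.
- *Sorafenib is under-dosed by the same route.* None of the three events in the working triggers a sorafenib reduction under Table 5. Only discretionary changes remain.
- *Grade 2 diarrhea makes the problem common.* Table 5 does say "For Grade 2 only, reduce selinexor one dose level (Table 3) until resolved", but that reduction is temporary and orders no hold. The background figures, "common Grade 1/2 TEAEs were diarrhea (82%), anorexia (78%), nausea (74%), and fatigue (65"%), pool grades 1 and 2 and give no reduction rate.
- *The level is barely received.* The 340 mg case needs an early lasting reduction and two missed doses. With all six doses taken the patient has 83% of plan, more milligrams than four full doses (400 mg, 67%), which the protocol accepts. The question is therefore how many doses were taken at the level under test; total exposure alone does not settle it.

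There are also safeguards. A cohort summary and Medical Monitor approval precede each change of level, the RP2D is chosen on safety and efficacy in discussion, and phase II monitors related non-hematologic grade 3/4 toxicity without the DLT duration limits. These soften the consequence. But Section 3.2 does not require the dose received to be reported, and none of them alters the 3+3 count. The phase II rule is a partial backstop: at 40% toxicity and 35% response, Table 8 gives a 0.3957 chance of early stopping, futility stops included.

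**Conclusion.** The point holds for selinexor through Table 5, and it should be fixed. It rests on the text: evaluability is by count, some non-DLT toxicities lead to reduction in cycle 1, and nothing removes or reassigns the patient. The direction is upward, given only that DLT risk does not rise as dose falls.

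The size is unknown, because the documents give no cycle 1 reduction rate. The rise from 23% to 35% (49% with two under-dosed patients in each three) depends on the assumed 40% and 20% risks and on the assumed frequency of reduction. A reader might instead take the chance of 0/3 or 1/6, which moves from 31% to 42% on the same inputs. That is the rule for moving up a level; for the top level, +1, the MTD definition needs six treated patients with at most one DLT. Nor do the documents show that the MTD will in fact be too high. They show that the counting rule permits an error in that direction and gives no means of seeing it.

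**What to change.** In Section 5.1.1.5:
- Count toward the minimum only doses taken at the assigned level of each drug.
- State that a patient with a DLT is evaluable whatever the number of doses. Read literally, the present text would replace a patient whose DLT ended dosing early, while Section 3.4 replaces only those who stop for non-toxicity reasons; the two must be reconciled.
- Replace a patient without a DLT who falls below the minimum.

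In the Section 3.2 cohort summary, list every such patient with the reason for reduction and the cycle 1 milligrams received. This matters because replacement alone takes poor tolerability out of the count. If the patients who are reduced are also the more susceptible ones, some upward bias remains, and the list makes it visible to those approving the next level.

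The cost is a few sentences and possibly one or two more replaced patients, which presses on the stated phase I maximum of 12. No dose-adjustment rule changes.
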